10.2. Appendix: PSA kinetics [Appendices](#)

PSA velocity is defined as the slope of the linear regression line of PSA against time in month.

PSA slope is the slope of the linear regression line of natural log of PSA against time in month.

PSA doubling time is defined as the natural log of 2 divided by the slope of the linear regression line of the natural log of PSA against time in month

As a numerical example

Date	PSA	Log _n	Log ₂
5/1/2016	0.5	-0.69	-1.00
6/1/2016	1	0.00	0.00
7/1/2016	0.6	-0.51	-0.74
8/1/2016	1	0.00	0.00
10/1/2016	1.6	0.47	0.68
PSA Slope	0.20	PSA Doubling Time	3.49 months
PSA Velocity	0.19 ng/ml/mo		

10.3. Appendix: Time to Event Data Analysis Censoring Rules

The specific programming specifications and censoring rules for PFS/rPFS will be defined in the Analysis Programming Specification.

Additionally, During the global pandemic of COVID-19, if a patient has missed 2 or more tumor assessments for causes related to COVID-19 (if the causes were identifiable and verified from any source), the patient may not be censored at the last objective tumor assessment, and the subsequent available tumor assessments can be used to determine an event of disease progression or as the censoring point.

10.4. Appendix: Immune-related Response Criteria per RECIST 1.1 (irRECIST)

Immune-related progressive disease (irPD) needs to be confirmed by a second, consecutive assessment at least 4 weeks apart. irPD is also considered to be confirmed if the patient:

- dies within 12 weeks after the initial observation of irPD, or
- discontinues treatment due to disease progression (clinical deterioration without radiological documentation) prior to or within 12 weeks after the assessment of irPD.

Immune-related Best Overall Response (irBOR) will be derived based on reported lesion responses at different evaluation time points from the start date until confirmed immune-related disease progression per irRECIST, according to the following rules.

[figure not shown]
- Confirmed irCR = at least two determinations of irCR at least 4 weeks apart before irPD.
- Unconfirmed irCR = one determination of irCR before irPD (and not qualifying for confirmed irCR or irPR).
- Confirmed irPR = at least two determinations of irPR or better at least 4 weeks apart before irPD (and not qualifying for confirmed irCR).
- Unconfirmed irPR = one determination of irPR before irPD (and not qualifying for confirmed irCR or irPR or unconfirmed irCR).
- irSD = at least one irSD or irPD assessment ≥ 6 weeks after start date and before confirmed irPD (and not qualifying for confirmed/unconfirmed irCR or irPR).
- irPD = ≤ 12 weeks after the first dose of study treatment and at least two consecutive determinations of irPD at least 4 weeks apart. irPD is also considered to be confirmed if the patient:
 - dies within 12 weeks after the initial observation of irPD, or
 - discontinues treatment due to disease progression (clinical deterioration without radiological documentation) prior to or within 12 weeks after the assessment of irPD.
- NE: All other cases.

Only tumor assessments performed before the start of any further anti-cancer treatment will be considered in the assessment of irBOR.

Immune-related Objective Response (irOR) is defined as irCR or irPR according to irRECIST from start date until confirmed irPD or death due to any cause. Both irCR and irPR must be confirmed by repeat assessments performed no less than 4 weeks after the criteria for immune-related response are first met. Also, irPD must be confirmed by a

second, consecutive assessment at least 4 weeks apart. Immune-related OR rate (irORR) is the proportion of patients with irOR in the analysis set.

CCI

Immune-related DC rate (irDCR) is the proportion of patients with irDC.

Immune-related Duration of Response (irDR) is defined, for patients with an immune-related objective response, as the time from first documentation of immune-related objective response (irCR or irPR) to the date of first documentation of irPD (which is subsequently confirmed) or death due to any cause. If a patient has not had an event (irPD or death), irDR is censored at the date of last adequate tumor assessment. The censoring rules for irDR are as described below for irPFS.

$$\text{irDR (months)} = [\text{date of event or censoring} - \text{first date of irOR} + 1]/30.4375$$

Immune-related Time to response (irTTR) is defined, for patients with an irOR, as the time from the start date to the first documentation of immune-related objective tumor response (irCR or irPR) which is subsequently confirmed.

$$\text{irTTR (in months)} = [\text{first date of irOR} - \text{start date} + 1]/30.4375$$

Immune-related Progression-Free Survival (irPFS) is defined as the time from start date to the date of irPD or death due to any cause, whichever occurs first. irPFS data will be censored on the date of the last adequate tumor assessment for patients who do not have an event (confirmed irPD or death), for patients who start a new anti-cancer therapy prior to an event or for patients with an event after two or more missing tumor assessments. Patients who do not have a baseline tumor assessment or who do not have any post-baseline tumor assessments will be censored on the start date unless death occurred on or before the time of the second planned tumor assessment in which case the death will be considered an event.

The censoring and event date options to be considered for the irPFS and irDR analysis are presented in [Table 2](#).

Table 2. Outcome and Event Dates for irPFS and irDR Analyses

Scenario	Date of event/censoring	Outcome
No baseline assessment	Start date	Censored ^a
irPD (subsequently confirmed) or death ≤16 weeks after last tumor assessment or ≤16 weeks after start date	Date of first irPD or death	Event ^b
irPD (subsequently confirmed) or death >16 weeks after the last tumor assessment	Date of last adequate assessment	Censored
Treatment discontinuation due to 'Disease progression' (clinical deterioration without radiological documentation) prior to or within 12 weeks after the assessment of first irPD	Date of first irPD	Event
New anti-cancer therapy prior to confirmed irPD	Date of last adequate assessment before anti-cancer therapy is given	Censored
irPD not confirmed or no irPD	Date of last adequate assessment	Censored

^a However if the patient dies ≤8 weeks after start date the death is an event with date on death date

^b irPD is also considered to be confirmed if the patient dies within 12 weeks after the initial documentation of irPD

The analyses for irBOR, irOR, irDR, irDC, irTTR will follow the methodology outlined for the RECIST 1.1 endpoints as follows

- irOR will be summarized but no formal test of hypotheses will be performed (only 95% CIs will be reported)
- irBOR, irOR, irDC, irDR, irTTR and irPFS will be summarized as described in Sections xx, for RECIST endpoints but irDR and irPFS will be analyzed using the censoring rules described in Table 2.

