5.6. Evaluable Population

As a consequence of its mechanisms of action, PrCa VBIR may require time after administration to induce a prostate cancer-specific immune response and subsequent tumor response. Therefore, tumors in patients treated with cancer vaccines may show early progression followed by subsequent response, therefore, supportive analysis populations may be based on the evaluable population (EP) which will consist of all patients in the mITT

population who have been dosed through Cycle 1 Day 57, Day 85 or Day 113 (Day 113 is Cycle 2 Day 1). To implement this, 3 sub-populations will be created: EP C1D57, EP C1D85, and EP C2D1. EP C1D57 will include all patients who have received all assigned doses at least until C1D57. EP C1D85 and EP C2D1 are defined in the same manner.

Additionally, tumor response and PD analyses may be repeated in the mITT population in patients who have no major protocol deviations during the first and second treatment cycle.

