8.1.3. Exploratory (Part A) / Secondary (Part B) Efficacy Analyses

In this First-In-Patient study anti-tumor activity is an exploratory objective. The main analysis populations will be based on mITT and EP.

Tumor response, using RECIST, irRECIST, will be presented in the form of patient data listings which include, but are not limited to tumor response assessed in comparison to baseline. Traditional response measures in solid tumors, such as ORR and PFS were developed to evaluate chemotherapies and can be unreliable for tracking response to immunotherapies such as cancer vaccines. For example, apparent tumor burden may increase during the first few months of cancer vaccine treatment because of inflammation/T cell infiltration into tumors even in patients who go on to have durable responses. Time to progression and number of patients with progression could be calculated from first vaccination (Cycle 1 Day 1), but may also be calculated excluding those progressions that happened before some specific timepoints (eg, Day 57, Day 113). Time to response will be calculated from first vaccination (Cycle 1 Day 1) to time of first response (ie, CR or PR).

Additionally, total measurable tumor burden will be evaluated by the irRECIST criteria that include responses after disease progression that are not captured by RECIST evaluation criteria in solid tumors.

For tumor response data, the following analyses may be performed:

1. Tumor response (CR, PR, SD, PD, etc.) by cohort and visit, separately for RECIST 1.1 and irRECIST. Investigator provided tumor response will be presented by descriptive statistics (frequency and percentage).
2. Best overall response, by cohort, **across all available tumor assessments from both treatment period and maintenance period**, separately for RECIST 1.1 and irRECIST. Best overall response will be derived programmatically. In the tabular data presentation, a row of CR+PR will be added to show the results of ORR. With RECIST 1.1, tumor response (CR or PR) confirmation is optional as response rate is not the primary endpoint of the study, hence unconfirmed best overall response will be derived and presented. With irRECIST, tumor response (irCR or irPR) and disease progression (irPD) are required to be confirmed, however in this study tumor response confirmation is not required, therefore unconfirmed best overall response will be derived and presented. Descriptive statistics (frequency and percentage) will be provided.

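### SAP 10.4's four irBOR response rules stop at irPD rather than confirmed irPD, so a confirmed response first seen after an unconfirmed irPD is scored irSD in irBOR but counts as a response under irOR

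*SAP*

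**What the plan says.** SAP 10.4 lists the irBOR categories in order. The two confirmed-response rules read "Confirmed irCR = at least two determinations of irCR at least 4 weeks apart before irPD" and "Confirmed irPR = at least two determinations of irPR or better at least 4 weeks apart before irPD". The unconfirmed irPR rule reads "Unconfirmed irPR = one determination of irPR before irPD", and the unconfirmed irCR rule has the same cut-off.

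Three other statements in the appendix use a different cut-off:

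- The lead-in to the list says that irBOR is "derived based on reported lesion responses at different evaluation time points from the start date until confirmed immune-related disease progression per irRECIST".
- The stable-disease rule in the list reads "irSD = at least one irSD or irPD assessment ≥ 6 weeks after start date and before confirmed irPD".
- Objective response (irOR) is "irCR or irPR according to irRECIST from start date until confirmed irPD or death due to any cause". It also requires the response to be confirmed at least 4 weeks later, and irORR is the proportion of participants with irOR.

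SAP 8.1.3 says that best overall response is derived by program, separately for RECIST 1.1 and irRECIST, with a CR+PR row that shows the response rate. For irRECIST it reports unconfirmed best response.

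**The concern.** The reason given for using irRECIST is that response may follow apparent progression. SAP 5.6 says "tumors in patients treated with cancer vaccines may show early progression followed by subsequent response", and SAP 8.1.3 says "total measurable tumor burden will be evaluated by the irRECIST criteria that include responses after disease progression that are not captured by RECIST". A rule that closes the response window at the first irPD call discards some of the responses that the criteria were adopted to catch. It also lets two summaries of one Cohort 3B secondary endpoint (Protocol 2.3, SAP 6.5) classify the same participant differently. The design makes such sequences possible: scans are every 8 weeks, and the text under Protocol Figure 1 encourages participants to stay on treatment for at least 24 weeks before removal for progression is considered.

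**Working it through.** The plan gives no figure on this point, so the check applies the rules to example sequences.

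**Inputs**

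- Scan times (Protocol Schedule of Activities, tumor assessment footnote): every 8 weeks ± 5 days, the first at 8 weeks. The first scan falls on day 56 ± 5, that is day 51 to 61, or 51/7 = 7.3 to 61/7 = 8.7 weeks. An irPD or irSD call at that scan always meets the 6-week condition of the irSD rule.
- Confirmation of response (SAP 10.4): two determinations at least 4 weeks apart. Scans 8 weeks apart satisfy this.
- Cohort 3B size (Protocol 9.3, SAP 4.3): 18.

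**Step 1: what irPD means inside the list.** The irSD rule accepts an irPD assessment that comes before confirmed irPD. That is possible only if irPD there means a single-visit call. The irPD category likewise asks for two consecutive determinations of irPD. Within the list, then, the unqualified word denotes one visit.

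**Step 2: apply the rules.** In each sequence the irPD is never confirmed: no second consecutive irPD, no death within 12 weeks of it, and no discontinuation for clinical progression prior to it or within 12 weeks after it. Visits are 8 weeks apart, starting at week 8.

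| Sequence | irBOR as written | irBOR to confirmed irPD | irOR |
|---|---|---|---|
| irPD, irPR, irPR | irSD | confirmed irPR | responder |
| irPD, irCR, irCR | irSD | confirmed irCR | responder |
| irSD, irPD, irPR, irPR | irSD | confirmed irPR | responder |
| irPR, irPD, irPR, irPR | unconfirmed irPR | confirmed irPR | responder |
| irPD, irPR only | irSD | unconfirmed irPR | not a responder |

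The results are the same for a first scan on day 51, 56 or 61.

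For the first row, both irPRs (weeks 16 and 24) follow the week-8 irPD, so neither irPR rule is met. The week-8 irPD is at 6 weeks or later and precedes any confirmed irPD, so the irSD rule is met.

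The last row gives no irBOR/irOR mismatch, because irOR needs confirmation. The fourth row keeps the participant in the unconfirmed irCR+irPR row of SAP 8.1.3 but loses the confirmed status.

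One exception to the irSD label: an unscheduled irPD at week 5, followed directly by two irPRs, is NE as written, a confirmed irPR with the confirmed cut-off, and a responder under irOR.

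**Step 3: direction.** The first irPD call can never come after confirmed irPD. The literal window therefore lies inside the window to confirmed irPD and can only lose response determinations.

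**Step 4: size.** One participant dropped from the response count changes the rate by 1/18 = 5.6 percentage points in Cohort 3B.

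**The case against.** The best defence is that irPD is shorthand for confirmed irPD. Protocol Appendix 4 builds confirmation into the definition of irPD, and SAP 10.4 opens by requiring it. The irDR and irPFS text uses the bare term for the confirmed event in places, and the irBOR lead-in already runs to confirmed progression. That may well be the intent. It does not remove the conflict, because the irSD rule in the same list sets an irPD assessment against confirmed irPD. A programmer who follows the bullets would produce the left-hand column of the table. If the defence is right, the fix merely writes the intent down.

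Other points on that side stand and limit the finding:

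- A reader might infer that everyone who responds after an unconfirmed irPD is irSD in irBOR and a responder in irOR. The documents do not support that. The mismatch with irSD needs a response that first occurs after the irPD and is then confirmed, as the last two rows of the table show.
- A reader might infer that irBOR loses all the delayed responses that irRECIST is meant to capture. It does not. Under Protocol Appendix 4, new lesions or non-index progression need not amount to irPD. Participants with RECIST 1.1 progression who never meet irPD keep their responses under either reading.
- A reader might blame this wording for any gap between the irCR+irPR row and irORR. SAP 8.1.3 reports unconfirmed responses and SAP 10.4 requires confirmed ones for irOR, so those two can differ whichever cut-off is used.
- No hypothesis is tested, the tabulations are optional, and the by-patient listings would still show a delayed response. The inclusion criteria for Cohort 3B require only about 40% or more of participants to have a measurable lesion (0.40 × 18 = 7.2, about 7 of 18), so few may be able to show the pattern.

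**Conclusion.** The point holds as an internal conflict in SAP 10.4. Taken literally, the four response rules score a confirmed response that first appears after an unconfirmed irPD as irSD, while irOR counts it. They also reduce irPR-irPD-irPR-irPR to unconfirmed irPR in irBOR. The effect runs one way: a lower irBOR-based response rate or a downgraded confirmation status. Each participant dropped is worth 5.6 points in Cohort 3B, if all 18 enrolled participants are in the denominator. The documents do not show how many participants would be affected, so 5.6 points is the weight of one case and not an estimate of bias. The conclusion rests on reading irPD in the list as a single-visit call, which the irSD rule supports, and on the irPD not being confirmed by any of the routes in SAP 10.4. The endpoint is secondary and descriptive, so this should be corrected before programming but does not threaten the trial's primary safety objective.

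**What to change.** In SAP 10.4, replace *before irPD* with *before confirmed irPD* in the confirmed irCR, unconfirmed irCR, confirmed irPR and unconfirmed irPR rules. Add a sentence stating that an irPD not subsequently confirmed does not end the search for response.

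Add a programming check that the number of participants with confirmed irCR or irPR in irBOR equals the number with irOR. Do not run it against the unconfirmed irCR+irPR row of SAP 8.1.3, which can legitimately exceed the irOR count; whether irRECIST response needs confirmation is a separate conflict between 8.1.3 and 10.4.

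The cost is one word in four rules, one sentence and one check. No new data are needed.

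### The irRECIST response rate counts unconfirmed responses in SAP 8.1.3 but only confirmed ones in SAP 10.4

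*SAP*

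**What the plan says.** SAP 8.1.3 (efficacy analyses, item 2) plans a best overall response table by cohort, produced once for RECIST 1.1 and once for irRECIST, in which "a row of CR+PR will be added to show the results of ORR". For irRECIST it acknowledges that the criteria normally call for confirmation, then sets this aside: "however in this study tumor response confirmation is not required, therefore unconfirmed best overall response will be derived and presented".

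SAP Appendix 10.4 says the opposite about objective response: "Both irCR and irPR must be confirmed by repeat assessments performed no less than 4 weeks after" the criteria are first met. It then states: "Immune-related OR rate (irORR) is the proportion of patients with irOR in the analysis set". irTTR runs to the first "immune-related objective tumor response (irCR or irPR) which is subsequently confirmed". irDR is defined only for participants with an immune-related objective response, so it inherits the same requirement. The best overall response list in the same appendix does keep separate unconfirmed categories, for example "Unconfirmed irPR = one determination of irPR before irPD".

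The appendix ends by saying that the immune-related endpoints "will be summarized as described in Sections xx, for RECIST endpoints"; the section number was never filled in.

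Protocol Appendix 4, Table 8 footnote b, requires irCR and irPR to be confirmed by a second assessment at least 4 weeks apart. Antitumor response by irRECIST is a Part B secondary endpoint for Cohort 3B (Protocol 2.3; SAP 6.5).

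**The concern.** A row labelled ORR in the irRECIST table and an endpoint called irORR will be read as the same quantity. As the SAP stands, the first counts every irCR or irPR seen once and the second counts only those seen again at least 4 weeks later. Two programmers working from different sections could report different rates for the same data. A participant shown as a responder in the best overall response table could also be missing from the irTTR and irDR summaries without explanation.

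The study is open label and the sponsor's team reviews data throughout (SAP 3). With 18 participants in Cohort 3B, the responder rule should be settled in the text rather than chosen once individual responses are known.

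**Working it through.** **The plan's only numerical ORR figure.** Protocol 9.3 says that 6 responders among 18, with a beta(0.5, 0.5) prior, give a posterior probability of about 80% that the true ORR exceeds 25%. The posterior is beta(6.5, 12.5), and 1 − F(0.25) = 0.797, so the figure reproduces. It concerns RECIST 1.1 ORR and does not bear on this point. The plan gives no figure for irORR.

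**The two rules side by side.** Take a participant with a first irPR.

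| What follows the first irPR | 8.1.3 CR+PR row | 10.4 irORR, irTTR, irDR |
|---|---|---|
| irPR or better at least 4 weeks later, before irPD | Responder | Responder |
| Treatment stopped within 6 weeks, no further scan | Responder | Not a responder |
| irPD at the next scan | Responder | Not a responder |

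**Whether the second row can occur.** Under the Schedule of Activities for Cohorts 3B and 5B (footnote 18), scans are every 8 weeks and end at permanent discontinuation. The End of Treatment scan is called for only if more than 6 weeks have passed since the last one. Someone who stops within 6 weeks of a first irPR therefore has no required confirming scan. Someone who stops later than that has a required scan more than 6 weeks after the first. This exceeds the 4-week minimum, so it can confirm.

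**Whether the third row can occur.** The 10.4 list itself provides for a single irPR before irPD and classes it as unconfirmed.

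**Size per participant.** The shift is 100/n percentage points.
- Cohort 3B, n = 18 (Protocol 9.3; SAP 4.3): 100/18 = 5.6 points.
- Cohorts 7A and 3B combined, as SAP 8.1.3 allows for selected analyses: 14 in 7A (Protocol 1.3.2, as of 11 November 2019) + 18 = 32, and 100/32 = 3.1 points.

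**Illustration.** Assume three participants in Cohort 3B with an irCR or irPR. The count is an assumption, and all 18 are taken to be in the analysis set. Intervals are exact (Clopper-Pearson) 95%.

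| Confirmed, of the three | 8.1.3 row | 10.4 irORR |
|---|---|---|
| 3 | 3/18 = 16.7% (3.6 to 41.4) | 16.7% (3.6 to 41.4) |
| 2 | 16.7% | 2/18 = 11.1% (1.4 to 34.7) |
| 1 | 16.7% | 1/18 = 5.6% (0.1 to 27.3) |
| 0 | 16.7% | 0/18 = 0% (0 to 18.5) |

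irTTR and irDR would then describe 3, 2, 1 or 0 of those participants.

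**Bound on who can contribute.** irPR needs measurable disease. Protocol 4.1.2 plans for at least approximately 40% of Part B participants under those criteria to have a measurable lesion. At that floor, 0.40 × 18 = 7.2, or about 7 participants. The actual number is not given.

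**The case against.** The strongest reply is that the two sections describe different outputs. Section 8.1.3 never uses the term irORR. It describes a best overall response table, in a list of analyses that may be performed, and it names the irRECIST confirmation rule before waiving it. The 10.4 list contains the unconfirmed categories that such a table needs. This stands in part: the table itself can be built from 10.4 without contradiction. It does not cover the label. The added row is called ORR and counts responses that 10.4 excludes from irORR, and nothing in the SAP says that two rates are intended.

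It may also be said that the waiver is deliberate and allowed. Protocol Section 9 lets the SAP modify the protocol's plans, and only major changes to the primary endpoint need an amendment. The Document History also records, under Amendment 3, a clarification to Appendix 4 that responses need not be confirmed. The log is not current text and its difference from footnote b is not an error, but it makes a deliberate waiver plausible. So a reader who infers that 8.1.3 is an impermissible departure from the protocol goes too far. What remains is that 10.4 was not brought into line with the waiver.

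Three other inferences are tempting and unsupported.
- **The unfilled cross-reference causes the conflict.** It points to summary methods for the RECIST endpoints, not to a confirmation rule. Filling it in would leave both rules standing.
- **A large share of responders would be lost.** The schedule shows that a response can go unconfirmed, but the documents do not say how often responders stop treatment within 6 weeks of a first response or progress at the next scan.
- **The main efficacy result for Cohort 3B is in doubt.** That endpoint is RECIST 1.1 ORR, for which 8.1.3 makes confirmation optional and plans the unconfirmed rate.

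**Conclusion.** The inconsistency is real and lies in the responder rule for the irRECIST response rate: unconfirmed in SAP 8.1.3, confirmed in SAP 10.4 for irORR, irTTR and, through irOR, irDR. Against the current protocol text (Appendix 4, Table 8 footnote b), 8.1.3 is the outlier, though the SAP may depart from the protocol on a non-primary analysis.

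Each participant with an unconfirmed response moves the Cohort 3B rate by 5.6 points. The total effect depends on how many there are, which the documents do not show, and could be zero.

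Severity is minor to moderate. The endpoint is secondary and descriptive with no hypothesis test, RECIST 1.1 ORR and the primary safety endpoint are untouched, and both rates can be recovered from the 10.4 best overall response categories.

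**What to change.** Use one responder rule for irORR, irTTR and irDR, and state it in both SAP 8.1.3 and 10.4.

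- **Preferred:** keep the confirmed definition in 10.4, which matches Protocol Appendix 4, Table 8 footnote b. Relabel the irRECIST row in 8.1.3 as *irCR+irPR, confirmed or unconfirmed*, and do not call it ORR.
- **If the 8.1.3 waiver is intended:** amend irOR, irORR and irTTR in 10.4 to unconfirmed response (irDR then follows through irOR), and state that this departs from footnote b.

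In either case, report the other rate as a labelled row. Separately, as an editorial correction, complete the missing section number at the end of 10.4.

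The cost is a few sentences and table labels. No new data are needed and almost no programming, because the 10.4 list already separates confirmed from unconfirmed responses. The one downside is that the reported irORR may be lower under the confirmed rule.
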